7.4.2. Progression of Disease to Cirrhosis

Investigators will closely monitor subjects for potential progression to cirrhosis at every visit (or at unscheduled visits). If the subject meets one or more of the criteria for potential progression to cirrhosis described in [Figure 3](#) and/or any additional evidence that may be available including findings from targeted physical exams or from clinically indicated procedures (eg, biopsy, ultrasound, or esophagogastroduodenoscopy [EGD]), then the subject is considered to have potentially progressed to cirrhosis; Child-Pugh scores must then be assessed. Refer to [Section 7.4.2.1](#) for determination of Child Pugh Score. If a subject may have progressed to cirrhosis, a Fibroscan assessment should be performed where possible (if not already part of the scheduled assessment) and repeated annually. Dose adjustments or investigational product discontinuation may be required in subjects who meet criteria for progression to cirrhosis (see [Table 4](#)). If the dose of investigational product is adjusted (Child-Pugh A) or if investigational product is discontinued (Child-Pugh B or C) a PK sample must be collected within 7 days. The PK sample should be collected prior to receiving the reduced dose.

[figure not shown]
If non-invasive indicators of progression to cirrhosis become evident at any time during the study, it is recommended that a liver biopsy should be obtained and sent for central reading to confirm the diagnosis of cirrhosis and for inclusion in the analysis of study outcomes. Any interpretations by a local pathologist should be collected and entered in the eCRF within 2 days of receiving results. If a biopsy is not performed, the reason should be stated in the eCRF. The following clinical outcomes may preclude the need for a liver biopsy to confirm progression to cirrhosis: presence of ascites, hepatic encephalopathy, variceal hemorrhage, or the presence of large esophageal varices or varices with a red wale that require treatment.

The process for assessing disease progression to cirrhosis, the potential need for liver biopsy, and the implications on dosing are summarized in [Figure 3](#).

Potential events of progression to cirrhosis will be reviewed and adjudicated by the Hepatic Outcomes Committee which is described in [Section 16.11](#). The Hepatic Outcomes Committee

charter describes the specific criteria for identification and adjudication of potential events of progression to cirrhosis.

Figure 3: Algorithm for Determining Progression to Cirrhosis

CP = Child-Pugh; INR = international normalized ratio; IP = investigational product; NFS = nonalcoholic fatty liver disease fibrosis score; TE = transient elastography; ULN = upper limit of normal.

Note: To maintain blinding, dose adjustments will be handled by the investigational product supplier such that:

- Subjects on OCA 25 mg have the dose reduced to OCA 10 mg
- Subjects on OCA 10 mg and placebo remain on OCA 10 mg and placebo, respectively

^a It is not necessary to rule out the occurrence of varices, ascites, or hepatic encephalopathy at each visit; however, if at any time during the clinical management of the subject there are signs and symptoms that are suggestive of any of these events (eg, ascites noted on ultrasound or presence of varices noted on clinically indicated EGD), then the subject is considered to have met the criteria for progression to cirrhosis and a Child-Pugh screen must be assessed for that subject.

7.4.2.1. Child-Pugh Assessment

The Child-Pugh (CP) Score (Pugh 1973, Lucey 1997) will be assessed only in subjects who meet one or more of the criteria for progression to cirrhosis (Figure 3). A targeted examination will be performed to assess ascites and hepatic encephalopathy. CP is calculated and reported within the electronic data capture (EDC) system based on data entered into the eCRF by adding the scores from the 5 factors outlined in Table 3 and can range from 5-15. Among subjects who meet criteria for progression to cirrhosis, dose adjustment (see Table 4) should be considered in those

with a CP score <7, and investigational product should be discontinued in those with a CP score \geq 7. For the purpose of dose adjustment or discontinuation, Child Pugh Scores should ONLY be applied in subjects who demonstrate progression to cirrhosis based on criteria presented in [Section 7.4.2](#). Dose adjustment or discontinuation should not be considered based solely on the CP score, in subjects who do not meet criteria for progression to cirrhosis.

Calculation of the CP score includes Investigator assessments of ascites and hepatic encephalopathy, which may be assessed during the AE review at the scheduled visits, as well as total bilirubin, serum albumin, and prothrombin time, which will populate from the central laboratory. The relationship of CP Score to disease progression is as follows:

- CP Score 5-6 = mild, well compensated disease (ie, CP Class A)
- CP Score 7-9 = moderate, significant functional compromise (ie, CP Class B)
- CP Score \geq 10 = severe, decompensated disease (ie, CP Class C)

Table 3: Child-Pugh Scoring System

Factor	Units	Points		
		1	2	3
Serum bilirubin	$\mu\text{mol/L}$	<34	34-50	>50
	mg/dL	<2.0	2.0-3.0	>3.0
Serum albumin	g/L	>35	28-35	<28
	g/dL	>3.5	2.8-3.5	<2.8
Prothrombin time	Seconds prolonged	0-3	4-6	>6
	INR	<1.7	1.7-2.3	>2.3
Ascites ^a		None	Mild	Moderate-Severe
Hepatic encephalopathy ^b		None	Grade 1 or 2	Grade 3 or 4

INR = international normalized ratio

West Haven criteria: [Vilstrup 2014](#); Child-Pugh criteria: [Pugh 1973](#), [Lucey 1997](#).

^a Refer to CTCAE [Appendix D](#) for definitions of severity of ascites

^b Grade 0: normal consciousness, personality, neurological examination, electroencephalogram
 Grade 1: restless, sleep disturbed, irritable/agitated, tremor, impaired handwriting, 5 cps waves
 Grade 2: lethargic, time-disoriented, inappropriate, asterixis, ataxia, slow triphasic waves
 Grade 3: somnolent, stuporous, place-disoriented, hyperactive reflexes, rigidity, slower waves
 Grade 4: unrousable coma, no personality/behavior, decerebrate, slow 2-3 cps delta activity

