Investigational product should **not** be interrupted in the following instances: 1) in subjects who previously experienced an event of symptomatic cholelithiasis and/or cholecystitis, and in whom symptoms have fully resolved at the present time while on investigational product; 2) in subjects who experience an event that is not symptomatic (such as an incidental finding of gallstones during an ultrasound exam); 3) in subjects who have already undergone a cholecystectomy following a prior event of cholelithiasis or cholecystitis (and who have no symptoms suggestive

of retained or recurrent bile duct stones); or 4) in subjects who have a medical history of pancreatitis and have not experienced a recurrence of pancreatitis since enrollment into the study.

Table 4: Criteria for Dose Adjustment, Interruption, Discontinuation and Rechallenge

DOSE ADJUSTMENT		
Criteria	Action Taken with IP	Rechallenge
Progress to cirrhosis and have Child Pugh A cirrhosis (CP score <7)	Adjust to a maximum daily dose of 10 mg (or equivalent placebo) in a blinded fashion	Not applicable. Remain at maximum daily dose of 10 mg (or equivalent placebo) for remainder of study.
≤Grade 2 Pruritus (refer to Section 15.1.5.1)	Drug holiday or less frequent dosing, as needed	Return to original daily dose if tolerated
DOSE INTERRUPTION		
Criteria	Action Taken with IP^a	Rechallenge^b
Liver laboratory values ^c are above the upper threshold criteria and signs and symptoms of hepatic injury are present ^d	Interrupt immediately upon initial observation	Subject may be rechallenged after a minimum of 30 days if abnormal liver enzymes return to below threshold values, there are no symptoms, laboratory abnormalities are determined not to be due to DILI and approved by the Medical Monitor and Investigator. If the liver enzymes do not return to below threshold values after 30 days and the Investigator considers that the event has not resolved, the Investigator should consult with the Medical Monitor to determine a treatment plan. This may include continuing close monitoring with interruption or discontinuing investigational product.
Liver laboratory values ^c are above the upper threshold criteria and there are no signs and symptoms of hepatic injury ^d	According to threshold limits (Table 2), either interrupt or interrupt after confirmation by repeat testing	

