Gastroenteritis (established severe abdominal pain, vomiting, diarrhea) or dehydration	Interrupt	If no evidence of liver injury is detected, IP may be restarted at the same dose after resolution of intercurrent illness.
AE categorized as ≥Grade 4 in severity and not or unlikely related to IP	Interrupt	
Potential renal impairment (serum creatinine exceeds upper threshold criteria [Section 7.6])	Interrupt after confirmation by repeat testing	Subject may be rechallenged after a minimum of 30 days if laboratory results return to within threshold criteria and approved by the Medical Monitor and Investigator.
Symptomatic cholelithiasis and/or cholecystitis	Interrupt	Subjects should remain in the study and complete all protocol-specified assessments, as defined in Table 1 , while off IP. Subjects may resume IP: 
 • After full resolution from a cholecystectomy and after receiving approval from the Investigator and Medical Monitor provided there are no signs or symptoms suggestive of retained or recurrent bile duct stones • If it is deemed, after surgical consultation, that the subject does not need to undergo surgery, symptoms have resolved, and after receiving approval from the Investigator and Medical Monitor.

Table 4: Criteria for Dose Adjustment, Interruption, Discontinuation and Rechallenge (Continued)

DOSE INTERRUPTION		
Criteria	Action Taken with IP^a	Rechallenge^b
Pregnancy	Interrupt	Subject should continue with the study visit schedule. The subject may re-start investigational product when she is no longer pregnant or breastfeeding at the discretion of the Investigator and after discussion with the Medical Monitor as described in Section 15.1.12 .
DOSE DISCONTINUATION		
Criteria	Action Taken with IP	Rechallenge
Potential Hepatic Decompensation ^c or Progression to Child Pugh B or C [CP Score \geq 7]	Discontinue ^g / No Rechallenge	Continue to return for scheduled study visits for safety follow up; however, the subject should not be rechallenged. Monitor closely for clinical outcomes according to protocol assessments.
Treatment-emergent acute or nonacute pancreatitis	Discontinue ^g / No Rechallenge	Continue to return for scheduled study visits for safety follow up; however, the subject should not be rechallenged.
\geq Grade 3 pruritus ^f		
Other AEs \geq Grade 3 considered possibly, probably, or definitely related to IP		
Liver transplantation		
Bariatric Surgery (Gastric Bypass)		

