AE = adverse event; ALP = alkaline phosphatase; ALT = aspartate aminotransferase; CP = Child-Pugh; DILI = drug-induced liver injury; IP = investigational product

^a If subject is unable to be evaluated promptly, study drug must be immediately interrupted.

^b Requires complete documentation of full resolution or normal/baseline based on laboratory parameters and symptoms.

^c ALT, ALP, direct or total bilirubin, or INR.

^d Signs and symptoms of hepatic injury include severe fatigue, nausea, vomiting, right upper quadrant pain, fever, rash, and eosinophilia.

^e Clinically evident complications of portal hypertension (eg, ascites, variceal hemorrhage, hepatic encephalopathy).

^f Severity per the current version of the CTCAE.

^g Subjects who permanently discontinue from investigational product are expected to continue in the study and should follow the regular visit schedule for the duration of the study. The Investigator should use clinical judgement to determine if more frequent assessments of laboratory tests and symptoms are necessary until stabilization of the clinical event leading to discontinuation has occurred (per discretion of the Investigator and upon discussion with the medical monitor).

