14. CLINICAL PHARMACOLOGY ASSESSMENTS

14.1.2. Subjects Who Develop Cirrhosis and Child-Pugh Class A

Subjects who develop cirrhosis and are Child-Pugh Class A (CP score <7) will have their dose adjusted (refer to [Table 4](#)). These subjects will provide 1 blood sample for PK assessment prior to dose adjustment, at the next scheduled visit. The PK assessment will measure serum concentrations of OCA, its conjugates (glyco-OCA and tauro-OCA), and OCA-glucuronide. The time of the last dose of investigational product and the time of the last meal will be recorded. The subject will then begin taking the adjusted dose of investigational product, thereafter, at the appropriate time.

14.1.2.1. Subjects Who Interrupt or Discontinue Investigational Product due to Cirrhosis or Hepatic Injury

Subjects who are considered to have potentially progressed to cirrhosis and discontinue investigational product due to progression to cirrhosis and due to Child Pugh score ≥ 7 or interrupt investigational product due to hepatic injury will provide a PK blood sample within ≤ 7 days from interruption or discontinuation of the investigational product (refer to [Table 4](#)).

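### A narrow group with a portal-hypertension complication but a Child-Pugh score below 7 falls under both dose adjustment and permanent discontinuation, and the Child-Pugh A adjustment is optional in one section and directive in two others

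*Protocol*

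**What the plan says.** - **Entry to scoring.** Footnote a of Figure 3 (Protocol 7.4.2) covers signs or symptoms suggestive of varices, ascites or hepatic encephalopathy: "then the subject is considered to have met the criteria for progression to cirrhosis and a Child-Pugh screen must be assessed for that subject".
- **Score rule.** Section 7.4.2.1 says: "Among subjects who meet criteria for progression to cirrhosis, dose adjustment (see Table 4) should be considered in those" with a score below 7, "and investigational product should be discontinued in those with a CP score" of 7 or more. It names no other stopping trigger.
- **Table 4, adjustment row (Section 7.7).** Subjects who progress to cirrhosis and "have Child Pugh A cirrhosis (CP score <7") get the action "Adjust to a maximum daily dose of 10 mg (or equivalent placebo) in a blinded fashion", and stay there for the rest of the study.
- **Table 4, discontinuation row.** The criterion is potential hepatic decompensation "or Progression to Child Pugh B or C". Either is enough, and there is no rechallenge. Footnote e, whose content fits this row, reads "Clinically evident complications of portal hypertension (eg, ascites, variceal hemorrhage, hepatic encephalopathy") and sets no score condition.
- **Section 14.1.2.** Subjects with cirrhosis and Child-Pugh Class A "will have their dose adjusted".
- **Continuing after an outcome event.** Section 7.1 allows it only while no Section 7.7 discontinuation criterion is met. Section 8.2.1 allows it while the investigator judges it safe.

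**The concern.** A site that follows Figure 3 footnote a, Section 7.4.2.1 and the first row of Table 4 keeps the subject on blinded adjusted dosing. A site that reads the decompensation row stops product for good. Under the softer wording of 7.4.2.1, a site could also leave the dose unchanged. For the same subject, all three can be defended from the text.

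Section 5.5 gives the reason this matters. In NASH subjects with compensated Child-Pugh A cirrhosis, plasma exposure was about 4- to 10-fold higher and liver exposure about 2-fold higher than in NASH subjects with fibrosis. Those figures show why the dosing instruction needs to be clear. They do not measure the effect of the conflict.

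The reading chosen also sets the last-dose date. The SAP builds the 30-day treatment-emergent window and the exposure-adjusted denominators on that date (SAP Sections 4, 10.3 and 10.4).

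**Working it through.** The plan gives no figure to reproduce. The check is whether Table 3 allows a portal-hypertension complication with a score below 7, and then what each rule says.

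**Inputs (Protocol Table 3).** There are five factors with 1 to 3 points each: bilirubin, albumin, prothrombin time/INR, ascites and encephalopathy. Mild ascites scores 2 and moderate-severe ascites 3. Encephalopathy Grade 1 or 2 scores 2 and Grade 3 or 4 scores 3. Variceal bleeding is not a factor. The minimum total is 5 × 1 = 5.

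**Scores with all three laboratory factors at 1 point** (order: bilirubin + albumin + INR + ascites + encephalopathy):

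| Presentation | Score | 7.4.2.1 and Table 4 row 1 | Table 4 decompensation row |
|---|---|---|---|
| Variceal hemorrhage only | 1+1+1+1+1 = 5 | Adjustment | Discontinue |
| Mild ascites only | 1+1+1+2+1 = 6 | Adjustment | Discontinue |
| Encephalopathy Grade 1 or 2 only | 1+1+1+1+2 = 6 | Adjustment | Discontinue |
| Moderate-severe ascites only | 1+1+1+3+1 = 7 | Discontinue (score rule) | Discontinue |
| Encephalopathy Grade 3 or 4 only | 1+1+1+1+3 = 7 | Discontinue (score rule) | Discontinue |
| Mild ascites plus Grade 1 or 2 encephalopathy | 1+1+1+2+2 = 7 | Discontinue (score rule) | Discontinue |

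**How narrow the overlap is.** Table 3 has 3^5 = 243 score patterns. Of these, 3^3 = 27 have neither ascites nor encephalopathy, so 243 − 27 = 216 have at least one. Only 2 of the 216 stay below 7: the two single-complication rows scoring 6 above.

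For variceal hemorrhage without ascites or encephalopathy, the score is the laboratory points plus 2. It stays below 7 in 4 of the 27 laboratory patterns: all three at 1 (score 5), or exactly one at 2 (score 6). These are counts of score patterns, not shares of subjects. The documents do not give the frequency of such presentations.

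**Is there a precedence rule in the readable text?** Section 7.1 leans toward stopping after an outcome event, because any Section 7.7 discontinuation criterion ends permission to continue. It does not settle the matter. Section 7.7 holds both Table 4 rows, and Section 8.2.1 uses the looser investigator-judgment standard. Sections 7.4.2, 7.4.2.1 and 14.1.2.1 tie discontinuation for cirrhosis to Child-Pugh B or C (score 7 or more).

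**Strength of the Child-Pugh A instruction.** Section 7.4.2.1 is optional (adjustment to be considered). Table 4 gives a plain directive, and Section 14.1.2 states the adjustment as certain.

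**The case against.** **Table 4 governs.** Section 7.7 says adjustments and discontinuations follow Table 4, and Sections 7.4.2, 7.4.2.1 and 14.1.2 refer to it. This helps with the optional wording in 7.4.2.1. It does not help with the overlap, because both competing rows are in Table 4. A reader may assume the stricter row prevails, but no readable passage says so.

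**The triggers differ.** Footnote a concerns suggestive signs and includes varices. Footnote e concerns clinically evident complications and names variceal hemorrhage. This stands in part: varices that have not bled are not clearly decompensation and are not counted here. It does not clear evident mild ascites, Grade 1 or 2 encephalopathy or a variceal bleed, and the row's own label says potential.

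**Sites do not act alone.** Sections 7.4 and 15.1.6.1 call for contact with the Medical Monitor when signs of decompensation appear. That limits the practical spread but supplies no rule.

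**Stronger readings that the documents do not support:**
- A reader might infer that any single complication with otherwise normal values scores below 7. The table above shows that the more severe grades score 7.
- A reader might infer that most of these subjects are having a primary-endpoint event. Encephalopathy counts only with hospitalization and West Haven 2 or more, ascites only if it needs medical intervention, and progression to cirrhosis only once adjudicated. Nothing in the documents supports most.
- A reader might count Section 7.4.2, which says adjustment or discontinuation may be required, as a further clash of strength. It covers both actions, and which one applies depends on the score, so it is not a clear conflict.
- A reader might treat the dose changing only in the 25 mg arm as a result of the conflict. Figure 3's note gives it as the blinded design.

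**Conclusion.** The passages contradict each other for a narrow group: mild ascites alone (CP 6), Grade 1 or 2 encephalopathy alone (CP 6), and variceal hemorrhage with near-normal laboratory values (CP 5 or 6). These subjects meet a row that keeps them on adjusted product and a row that stops it permanently. Separately, the Child-Pugh A adjustment is optional in Section 7.4.2.1 and directive in Table 4 and Section 14.1.2.

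The consequence is subject safety and uneven exposure between sites. A reader might infer that the primary test is compromised, and the documents do not support that. Dosing after a first event cannot change the time to that event, and SAP Section 2.3.2.1 handles dose adjustment, interruption and discontinuation by treatment policy, so later events still count.

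Two caveats apply. The body of Figure 3 is not shown and may contain a precedence rule; if so, the text must still be brought into line with it. The link between the decompensation row and footnote e is inferred from content, because the row's footnote marker cannot be read reliably. No view is taken here on which action is clinically right.

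**What to change.** Reconcile Protocol Sections 7.4.2, 7.4.2.1, 8.2.1 and 14.1.2, Figure 3 with its footnote a, and the two Table 4 rows:

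1. Make the adjustment and discontinuation rows mutually exclusive, and state one rule for a subject with a portal-hypertension complication and a Child-Pugh score below 7.
2. Use one strength of instruction, optional or mandatory, for the Child-Pugh A adjustment in every place it appears.
3. Confirm that the decompensation row points to footnote e, and align the conditions for continuing product after an outcome event in Sections 7.1 and 8.2.1.

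The clinical team decides which rule and which strength apply. The cost is protocol wording and a memo to sites, with no new procedure.

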7.4.2.2. Model for End-Stage Liver Disease (MELD) Scoring

MELD is a scoring system used to assess the severity of chronic liver disease. The MELD score is calculated using serum creatinine (mg/dL), bilirubin (mg/dL), and INR. The MELD-Na score is calculated using serum creatinine (mg/dL), bilirubin (mg/dL), INR, and sodium and is calculated when the MELD score is greater than 11. The MELD calculation adjusts for subjects who have had 2 or more dialysis treatments within the prior week and will automatically assign a serum creatinine of 4.0 mg/dL for these subjects.

7.4.3. Close Observation

The Investigator should consistently and frequently assess individual subjects who meet the above criteria to determine on an ongoing basis the totality of a subject's clinical profile, which includes careful evaluation of signs and symptoms of potential hepatic injury or decompensation coupled with rules-based laboratory monitoring. If investigational product is interrupted or discontinued as described in [Section 7.7](#), subjects should continue to be closely monitored based on the clinical judgement of the Investigator and evaluated for signs and symptoms of potential disease progression to cirrhosis or hepatic injury. In the event of potential hepatic injury, the subject should be promptly brought into the clinic and undergo a complete evaluation (laboratory assessments, physical examinations, and review of signs and symptoms). Subjects who permanently discontinue from investigational product are not required to undergo additional safety visits provided stabilization of the clinical event leading to discontinuation has occurred (per discretion of the Investigator and upon discussion with the Medical Monitor).

At a minimum, the following assessments should be conducted at each study visit:

- Exam and thorough review of subject-reported signs and symptoms of hepatic injury or decompensation ([Appendix C](#))
- Liver biochemistry (including ALP, ALT, AST, GGT, total and conjugated bilirubin, creatinine, and albumin), prothrombin time (PT)/INR, serum electrolytes, and assessment of algorithm for progression to cirrhosis (only if the subject is at the study site) and MELD scores

In addition, a PK sample for assessment of OCA serum drug levels and its major metabolites should be obtained in any subject who develops an AE of hepatic injury or decompensation or interrupts investigational product due to potential hepatic injury ([Section 7.4.1](#)). A PK sample should also be collected when the dose of investigational product is reduced (Child-Pugh A) or discontinued (Child-Pugh B/C) due to progression to cirrhosis ([Section 7.4.2](#)).

For events of potential hepatic injury, the following additional monitoring procedures should be performed per FDA Guidance for Industry on Drug Induced Liver Injury. These cases need to be discussed with the Sponsor's Medical Monitor:

- Repeating liver enzyme and serum bilirubin tests as described in [Table 2](#)
- Obtaining a more detailed history of symptoms and prior or concurrent diseases
- Obtaining a history of concomitant drug use (including nonprescription medications and herbal and dietary supplement preparations), alcohol use, recreational drug use, and special diets is important. Concomitant drugs with potential hepatotoxicity should be recorded and discontinued unless alternative therapies are not available. In the case of concomitant drugs that are potentially hepatotoxic, continued use of investigational product should be discussed with the Sponsor's Medical Monitor. The subject may be discontinued from investigational product, if clinically appropriate
- Obtaining a history of exposure to environmental chemical agents or herbal supplements that may be associated with liver toxicity

- Ruling out acute viral hepatitis types A, B, C, D (in those thought to have acute HBV infection), and E; autoimmune or alcoholic hepatitis; Wilson's disease, hypoxic/ischemic hepatopathy; and biliary tract disease
- Obtaining additional tests to evaluate liver function, as appropriate (eg, INR, direct bilirubin)
- Seeking hepatology consultation, if the Investigator is not a hepatologist

For all subjects in whom close monitoring is initiated for potential hepatic injury, a follow-up assessment of the subject's status should be performed after approximately 12 months of monitoring.

